8.4.3.3 EXPECTEDNESS

Anticipated adverse device effect is an effect which by its nature, incidence, severity or outcome has been identified in the risk assessment.

An **unanticipated** serious adverse device effect (USADE) is a serious adverse device effect which by its nature, incidence, severity or outcome has not been identified in the current version of the risk assessment.

An **unanticipated** adverse device effect (UADE) means any serious adverse effect on health or safety or any life-threatening problem or death caused by, or associated with, a device, if that effect, problem or death was not previously identified in nature, severity, or degree of incidence in the investigational plan or application (including a supplementary plan or application), or any other unanticipated serious problem associated with a device that relates to the rights, safety, or welfare of participants.

8.4.4 ADVERSE EVENT REPORTING

Adverse events will be recorded on the AE eCRF.

8.4.5 SERIOUS ADVERSE EVENT REPORTING

The reporting requirements are as follows:

- In the event of a Serious Adverse Event (SAE) Investigators are required to report to Sponsor within 24 hours of becoming aware of the SAE.
- SAE reporting will be performed per the IRB and any local requirements.
- SAEs will be assessed by the Sponsor to determine if the event is a UADE. Any UADE will be reported to the FDA and IRB as soon as possible, but no later than 10 working days after the Sponsor first learns of the effect, as required by 21 CFR Part 812.

9 STATISTICAL METHODS

9.1 GENERAL CONSIDERATIONS

Data will be summarized using descriptive statistics unless specific hypothesis testing is specified. Means, standard deviation, median and range will be summarized for continuous data and counts and frequencies for categorical data. Data analyses will be performed using a validated statistical software package such as Stata (College Station, TX) or SAS (Cary, NC). No imputation for missing data will be performed other than for the sensitivity analysis of the primary endpoint.

9.2 POPULATIONS FOR ANALYSIS

The study has a single test population that will be enrolled according to the inclusion/exclusion criteria.

Intent-to-treat (ITT): All participants that are randomized.

Modified intent-to-treat (mITT): All participants that are randomized and receive any ECP compressions from either device. Group assignment will be the randomized treatment order even if therapy was delivered not according to randomization.

Safety Cohort: Same as the mITT. Only participants that receive any ECP compressions from either device will be included.

Per protocol (PP): Participants that are randomized and receive any ECP compressions from both devices, are treated as they are randomized, and have no major deviations (i.e., inclusion/exclusion criteria, randomization, affect participant safety or validity of primary endpoint).

9.3 ENDPOINTS AND STATISTICAL ANALYSES

9.3.1 PRIMARY EFFECTIVENESS ENDPOINT

There is a single primary endpoint for this trial for effectiveness. Safety will be summarized under secondary endpoints with no hypothesis testing.

Primary Effectiveness Endpoint:

The average DA ratio will be calculated by a blinded evaluator for the 8th minute (i.e., between minute 7 and minute 8) of treatment with each ECP device tested for each participant via the Waveform Analysis Charter. The 8th minute was selected as the pilot data indicated participants

moved more in the last minute of therapy and more signal noise was present. Each participant will have a single average DA ratio per system (i.e., two values per participant).

The difference of the average DA ratio attained using the Wave PRO and the predicate device will be calculated for all randomized study participants with paired ECP data.

Hypothesis:

Null Hypothesis: Wave PRO is inferior to the predicate ECP device

$H_0: \mu_P - \mu_p \leq -0.15$

Alternative hypothesis: Wave PRO is not inferior to predicate ECP device

$H_a: \mu_P - \mu_p > -0.15$,

where μ_P is the mean diastolic ratio for Wave PRO and μ_p is the mean diastolic ratio for the predicate ECP, and -0.15 is the non-inferiority margin.

Sample size calculation:

Based on preliminary internal data, the observed mean difference between Wave PRO and the predicate ECP was 0.05 ± 0.23 , but we will assume a true difference of 0 with a standard deviation of 0.30 for sample size calculations.

Table 1: Summaries for the predicate and Pression Wave Pro ECP pilot data.

	Predicate ACS	PRESSION Wave Pro ECP	Difference (Wave Pro– ACS)
Diastolic ratio (N=7)	0.93± 0.12	0.98 ± 0.19	0.05 ± 0.23

Assuming a true difference of 0 with the inflated standard deviation of 0.30, a sample size of 44 participants is adequate to test the non-inferiority hypothesis with at least 90% power and a 1-sided alpha of 0.025. Allowing up to 12% attrition for missing data, approximately 50 participants may be enrolled and undergo ECP compressions in order to have at least 44 participants with paired data.

Selection of non-inferiority margin:

The non-inferiority margin of -0.15 was selected for the difference in diastolic ratio as it seemed a reasonable number. DA ratio characterizes the hemodynamic effect of ECP and is predictive of CCS angina class improvement. The weighted mean DA ratio calculated using published values for predicate ECP devices is 0.79 ± 0.46 (N = 5600). Pression has utilized accepted biostatistical study design principles to calculate the sample size of the clinical study to reach adequate power to prove substantial equivalence (non-inferiority) of the Wave PRO compared to predicate ECP devices using the literature.

The proposed sample size aligns with the 20-50 number of participants previously suggested by FDA at the Pression pre-submission meeting on 8 November 2021.

Analysis cohort:

The primary analysis will use the participants in the mITT cohort that have paired data (an average DA ratio from each system). The primary analysis will not include any imputation for missing data (see missing data section below for planned sensitivity analysis).

A supplemental analysis of the primary endpoint will be conducted for the participants in the Per Protocol cohort with paired data.

Analysis methods:

Along with descriptive statistics, an analysis of variance (ANOVA) model for crossover design will be performed. This ANOVA model includes sequence, participant within sequence, period, treatment, and period by treatment interaction factors. The least square (LS) mean of each treatment and its 95% confidence interval (CI) will be presented. A pairwise difference between two treatments (Wave PRO – predicate ECP) in the treatment LS mean and its 95% CI will be constructed. If the lower bound of this 95% confidence interval is greater than -0.15, then we will reject the null hypothesis and conclude that Wave PRO is not inferior to the predicate ECP. A *p*-value will be constructed using the LS means parameter estimates and standard error to test the hypothesis.

A simple paired Student's *t*-test will also be constructed for the difference of Wave PRO – predicate ECP to test if greater than -0.15.

Missing Data and Imputations:

Every effort will be made to obtain required data at each scheduled evaluation from all participants who have been randomized. In situations where it is not possible to obtain all data, it may be necessary to impute missing data for the primary endpoint. Missing mean diastolic ratio for each ECP may need to be imputed and analyzed in a sensitivity analysis.

A sensitivity analysis will be conducted, imputing missing ECP mean DA ratios utilizing a Markov Chain Monte Carlo multiple imputation procedure using treatment group as a covariate. For this method, 5 imputation datasets will be prepared if more than 10% of data are missing for randomized participants. These data will be analyzed by imputations using the same model described above and will be combined.

If an mITT participant is missing both ECP mean DA ratios (e.g., unable to tolerate ECP therapy of both devices), then the participant will be excluded from all primary endpoint analyses. Any participant unable to tolerate either ECP therapy will be summarized separately.

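### The 95% CI for each device's own mean DA ratio rests on an error term suited to the difference, so its coverage is in general not 95%

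*Combined protocol and SAP*

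**What the plan says.** The analysis methods in section 9.3.1 specify one model: "This ANOVA model includes sequence, participant within sequence, period, treatment, and period by treatment interaction factors". Two kinds of interval come from it. The first is per device: "The least square (LS) mean of each treatment and its 95% confidence interval (CI) will be presented". The second is the CI of the Wave PRO minus predicate difference, whose lower bound is compared with -0.15. Only the second decides non-inferiority. The synopsis (1.1) and the overall design (4.1) mention only the second.

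The section does not say whether participant is fixed or random, does not name the error term for the per-device intervals, and allows no device-specific variance.

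Table 1 of the same section gives pilot results for 7 participants: 0.93 with SD 0.12 for the predicate and 0.98 with SD 0.19 for Wave PRO. On the paired scale, "the observed mean difference between Wave PRO and the predicate ECP was 0.05 ± 0.23".

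**The concern.** Each participant contributes one value per device. Once participant is fitted as a factor, the residual measures only within-participant scatter, and one residual serves both devices. That is the right yardstick for the difference. A device's mean, taken as an estimate for the population, varies with that device's own SD across participants, and the model does not use that SD. Both devices therefore receive the same interval width, whatever their spread.

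At stake is how the device-level results read in a 510(k) file. If Wave PRO is the more variable device, its mean looks more precise than it is and the predicate's looks less precise. A reader may also set the predicate's interval beside the literature value in the same section ("The weighted mean DA ratio calculated using published values for predicate ECP devices is 0.79"), although the plan specifies no such comparison.

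**Working it through.** **1. The plan's own figure.** The planning inputs are: "we will assume a true difference of 0 with a standard deviation of 0.30 for sample size calculations", a margin of -0.15, and a design "with at least 90% power and a 1-sided alpha of 0.025". The normal approximation gives n = (1.960 + 1.282)² × 0.30² / 0.15² = 42.03, so 43. Exact noncentral t power (n - 1 df) is 89.3% at 43 and 90.0% at 44. The stated 44 is reproduced, and 44 / 0.88 = 50 reproduces the number randomized.

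**2. Inputs for the check.** SDs of 0.19, 0.12 and 0.23 from Table 1; 44 pairs from the sample size paragraph; 22 per sequence assumed. The implied within-participant correlation is (0.19² + 0.12² - 0.23²) / (2 × 0.19 × 0.12) = -0.0024 / 0.0456 = -0.05. Rounding in the table allows about -0.18 to 0.06.

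**3. Interval from the ANOVA, participant fixed.**
- Error SD = SD(difference) / √2 = 0.23 / √2 = 0.163.
- SE of either device's LS mean = 0.163 / √44 = 0.0245.
- Half-width = 2.018 (t, 42 df) × 0.0245 = 0.049 for both devices.

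**4. Interval from each device's own SD (t, 43 df).**
- Wave PRO: 2.017 × 0.19 / √44 = 0.058.
- Predicate: 2.017 × 0.12 / √44 = 0.036.

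The ANOVA interval is thus about 14% too narrow for Wave PRO and about 36% too wide for the predicate.

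**5. Coverage.** Approximately 2Φ(1.96 × 0.163 / SD) - 1, which is 0.907 for Wave PRO and 0.992 for the predicate. With participant random and a common variance, the pooled SD is √((0.19² + 0.12²) / 2) = 0.159, again between the two device SDs. Simulation of 40,000 trials gave:

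| Device SDs, correlation | Participant fixed (Wave PRO / predicate) | Participant random, common variance | Own SD |
|---|---|---|---|
| 0.19 / 0.12, -0.05 (pilot) | 91% / 99% | 90% / 99% | 95% / 95% |
| Equal, 0 (assumed) | 95% / 95% | 95% / 95% | 95% / 95% |
| Equal, 0.3 (assumed) | 90% / 90% | 95% / 95% | 95% / 95% |
| Equal, 0.5 (assumed) | 84% / 84% | 95% / 95% | 95% / 95% |

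Scaling the pilot SDs up so that the difference has SD 0.30 leaves the first row unchanged. The CI of the difference covers 95% in every row.

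**The case against.** The strongest reply is that the shortfall is not certain. The plan leaves the participant term open, and equal SDs with participant random, or equal SDs with zero correlation and participant fixed, give 95%. Seven participants do not establish unequal SDs: a Pitman-Morgan test on the Table 1 figures gives p of about 0.34. The pilot correlation of -0.05 also gives no sign of a between-participant component for the model to leave out. All of this stands, and it makes the point conditional.

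A reader might infer a much larger failure by giving both devices the literature SD of 0.46 with a difference SD of 0.30, which yields about 64% coverage. The documents do not support that reading. It needs a correlation of 1 - 0.30² / (2 × 0.46²) = 0.79, participant fixed, and a predicate literature SD that the plan never applies to Wave PRO. With participant random, coverage in that setting is 95%.

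It can also be said that each device's mean and SD will be reported descriptively (9.1 and 9.3.1), so a reader could rebuild the interval. That is true and limits the harm, but the printed interval would still be labelled 95%. Finally, with participant fixed and equal residual variances, the ANOVA interval is valid for the mean over the participants studied. The plan does not state that narrower target, and a device mean with a CI will ordinarily be read as describing the patient population.

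**Conclusion.** The point holds as a minor reporting correction. The per-device intervals are a stated output, and nothing in the plan ensures the conditions under which both have 95% coverage. On the plan's only device-level SDs for these two systems, coverage is about 91% for Wave PRO and 99% for the predicate under the fixed reading, and about 90% and 99% under the random reading with a common variance. This rests on the pilot SDs holding at 44 balanced pairs, and those SDs are imprecise.

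Two stronger conclusions do not follow. It cannot be said that the intervals will certainly miss 95%, because equal SDs under the conditions above would restore it. Nor is the trial's conclusion at risk: the decision rule uses only the CI of the difference, which keeps 95% coverage throughout, and the paired t-test and the sample size of 44 do not involve the per-device intervals.

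**What to change.** In the analysis methods of 9.3.1, keep the crossover ANOVA for the Wave PRO minus predicate difference and its CI. Add one sentence saying that each device's mean will be given with a 95% CI from that device's own SD (t, n - 1 df), or from a mixed model with participant random and a separate variance per device, and state which of the two will be used. If attrition leaves the sequences unequal, the mixed model keeps the period-adjusted LS mean, whereas the simple mean does not.

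The cost is one sentence and a small change to the analysis code, with no extra data and no loss of power. If the pilot SDs hold, the Wave PRO half-width rises from about 0.049 to 0.058 and the predicate's falls from about 0.049 to 0.036.

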9.3.5 SUB-GROUP ANALYSES

Descriptive statistics will be used to summarize primary and secondary effectiveness endpoint data by treatment arm and for the difference (Wave PRO – predicate ECP) for the following subgroups:

- Gender
- Age groups (above and below median)

- Race
- Fitzpatrick skin type

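### The only missing-data sensitivity analysis does not say whether imputation uses the participant's other DA ratio and device order, and it rests on 5 imputations

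*Combined protocol and SAP*

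**What the plan says.** The primary analysis in section 9.3.1 takes mITT participants with a DA ratio on both devices and imputes nothing. Section 9.1 allows imputation only in the sensitivity analysis of the primary endpoint. The per-protocol analysis also uses complete pairs, so the imputation analysis is the only planned check on missing data.

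That analysis is a "Markov Chain Monte Carlo multiple imputation procedure using treatment group as a covariate". When more than a tenth of the data are missing, "5 imputation datasets will be prepared". No other imputation variable is named. The completed datasets go through the primary model: "This ANOVA model includes sequence, participant within sequence, period, treatment, and period by treatment interaction factors". Participants with neither DA ratio are left out, so everyone who is imputed has an observed value on the other device.

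Two things are not stated.

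- **What treatment group means here.** Section 9.2 ties group assignment to the randomized order. Section 9.3.1, however, lists sequence and treatment as separate factors, and section 9.3.5 summarises results "by treatment arm and for the difference", where the arm is the device.
- **The data layout.** It could be one record per participant holding both ratios, or one row per session.

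**The concern.** In a crossover the participant's other measurement is usually the best predictor of a missing one, and the analysis model is built on that pairing. If treatment group means device and rows are imputed separately, a missing Wave PRO ratio is drawn around the Wave PRO mean, whatever that participant showed on the predicate. The imputation model is then poorer than the analysis model. It can bias the difference even when data are missing at random given the observed ratio, and it adds spurious within-participant scatter.

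What is at stake is how far the check can be trusted. If it disagrees with the primary result, nobody could tell whether missing data or the imputation model caused the disagreement. Because the wording allows several models, the choice could also be made after the data are seen.

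**Working it through.** **1. The plan's own figures.** The inputs, all from section 9.3.1, are "at least 90% power and a 1-sided alpha of 0.025"; "Assuming a true difference of 0 with the inflated standard deviation of 0.30"; a margin of -0.15; and "Allowing up to 12% attrition for missing data, approximately 50 participants may be enrolled".

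- Normal approximation: n = ((1.960 + 1.282) × 0.30 / 0.15)² = 42.03, so 43.
- Noncentral t: power at 44 pairs is 0.9000 for a paired test, and 0.8997 with the crossover's n - 2 degrees of freedom.
- 44 / (1 - 0.12) = 50.

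The plan's figures reproduce. Planned attrition corresponds to 6 of 50 participants without a pair.

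**2. Between-device correlation.** This uses the pilot SDs in Table 1 (0.12, 0.19, and 0.23 for the difference; N = 7).

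- ρ = (0.12² + 0.19² - 0.23²) / (2 × 0.12 × 0.19) = -0.0024 / 0.0456 = -0.053.
- Fisher z with SE 1/√(7 - 3) = 0.5 gives a 95% CI of -0.775 to 0.729.

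The pilot points to zero but rules out little. The values 0.3, 0.5 and 0.7 below are assumptions.

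**3. Why device-only imputation can be biased.** Assume equal SDs σ on both devices and an SD of the difference of 0.30, so σ = 0.30 / √(2(1 - ρ)). Let the 6 participants missing Wave PRO have predicate values S SDs below the average of all 50.

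- Their Wave PRO values are expected to lie ρSσ below average.
- The mean of the 44 observed values lies ρSσ × 6/44 above average, and the imputed values are drawn around it.
- Error per imputed value is ρSσ × 50/44. Over 50 participants the bias is (6/50) × (50/44) × ρSσ = (6/44)ρSσ.
- For S = 1 the bias is -0.001, +0.010, +0.020 and +0.037 at ρ = -0.05, 0.3, 0.5 and 0.7.

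**4. Simulation, Wave PRO more often missing when the predicate ratio is low.** The settings were 3,000 trials each, 50 participants in two equal sequences (the allocation ratio is assumed), 6 Wave PRO values missing, 5 imputations, Rubin's rules and a true difference of -0.15. Pass means a lower 95% limit above -0.15. Monte Carlo error on a 2.5% rate is about 0.3 points.

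| ρ | Device only: bias, pass | Both ratios + sequence: bias, pass | Complete pairs: bias, pass |
|---|---|---|---|
| -0.05 | -0.002, 2.5% | -0.001, 2.3% | -0.034, 0.5% |
| 0.3 | +0.011, 3.7% | -0.001, 2.2% | -0.027, 0.4% |
| 0.5 | +0.023, 5.1% | -0.000, 2.4% | -0.023, 0.7% |
| 0.7 | +0.040, 5.7% | -0.001, 2.2% | -0.019, 1.0% |

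When missingness follows the predicate value more tightly, the device-only bias is about +0.015, +0.030 and +0.054 at ρ = 0.3, 0.5 and 0.7. If predicate values are the missing ones, the sign reverses.

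**5. Missing completely at random.** There is no bias. The device-only mean SE over the true sampling SD is 0.0456/0.0448 = 1.02, 0.0479/0.0457 = 1.05 and 0.0524/0.0475 = 1.10 at ρ = 0.3, 0.5 and 0.7. A 12,000-trial repeat gave 1.02, 1.05 and 1.11. At ρ = -0.05 the ratio is 0.0435/0.0447 = 0.97. With both ratios and sequence in the model, at ρ = 0.7, it is 0.0452/0.0447 = 1.01.

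**6. Device order.** Assume a period effect of 0.10 and that all 6 missing values are Wave PRO given second. Bias is -0.007 to -0.009 for device only, and -0.006 to -0.012 when the other ratio is used without sequence. Adding sequence brings it within 0.0015.

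**7. Number of imputations.** Re-imputing the same data with different seeds moves the lower confidence limit with an SD of about 0.008 at 5 imputations and about 0.002 at 50. The first figure is 0.008/0.15, about 5% of the margin, and it arises even under a joint model.

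**The case against.** The benign reading is a fair one. Section 9.3.1 gives each participant two values and speaks of a participant missing both, which suggests one record with two variables. MCMC imputation on such a record uses each ratio to impute the other, and a covariate is then an addition. If group means randomized order, as in section 9.2, the plan already intends the model recommended below. A reader might infer that the plan fills missing values while ignoring the other ratio and the order. The documents do not say that; they leave it open.

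A reader might also take the device-only pass rates as the trial's false-positive rate. They are not. The non-inferiority decision uses complete pairs. In the scenario of step 4, complete pairs are biased against Wave PRO and pass 1.0% of the time or less at the margin, so no excess false claim follows.

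Three further limits stand.

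- The one correlation that can be derived from the documents is near zero, where the models agree.
- Nothing in the documents says Wave PRO values go missing because the predicate ratio is low. They mention movement noise and intolerance.
- The 10% trigger is unclear. Six participants each missing one value is 12% of participants but 6 of 100 DA ratios, so at planned attrition the imputation might not run.

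What remains is that the text fixes neither the group nor the layout, that a pilot of 7 cannot rule out a sizeable correlation, and that 5 imputations leave avoidable noise on any reading.

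**Conclusion.** The imputation model is underspecified, and one ordinary reading of it is poorer than the analysis model it feeds. On that reading, with 6 of 50 Wave PRO values missing, the effect is immaterial at the pilot-implied correlation. At assumed correlations of 0.3 to 0.7, the sensitivity estimate is off by about 0.01 to 0.05, roughly 7 to 33% of the 0.15 margin (0.01/0.15 and 0.05/0.15), in a direction set by the missingness mechanism. If data are missing completely at random, its SE is overstated by about 2 to 11%.

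These sizes rest on assumed correlations, equal SDs, equal allocation and assumed mechanisms. The primary decision is not affected. The loss is in the one analysis meant to show whether that decision is robust to missing data. This is a free improvement rather than a flaw in the main test.

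**What to change.** In section 9.3.1, replace the imputation sentence with wording to this effect: missing DA ratios will be imputed with one row per participant from a joint model containing both devices' DA ratios and the randomized sequence (which fixes the period of each device), using 50 imputed datasets and a fixed seed; each dataset will be analysed with the same crossover model and the results combined by Rubin's rules. The same edit can say whether the 10% trigger counts participants or DA ratios.

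The cost is a sentence or two and seconds of computing, with no new data, visits or participants. If the joint model was already intended, the edit simply records it. It should be made before database lock.
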